We will examine baseline characteristics (socio-demographic variables, medical and psychiatric comorbidity, duration of fibromyalgia, and current and prior pain treatments) of the POYSE sample. To evaluate the representativeness of study enrollees among all eligible patients, we will compare the enrollees and those who decline enrollment on their demographic characteristics. If there are systematic differences, these will be considered in the interpretation of the results of subsequent analyses. We will also examine differences in baseline characteristics between patients who remain in the study and those who dropout. Two-factor ANOVA models which include dropout status, treatment group (YOGA vs. SEP) and their interaction will be used for continuous variables. Logistic regression models with the same terms will be used for dichotomous variables.

D9c. Main analysis of the primary outcome (FIQR total score)

Our main analysis will employ a repeated measurement analysis of covariance (ANCOVA) model which is more powerful than two-sample t-test when the baseline outcome measurement is positively correlated with post baseline outcome.¹²¹ We plan an intent-to-treat analysis approach with the primary endpoint at 3 months and evaluation of “early” response at 1 month and “sustained” response at 3 and 6 months post-intervention. We will summarize this primary outcome at each time point (baseline, 1, 3, 6, and 9 months) for both arms. The difference between time points will be compared.

Since the primary outcome (FIQR total score) is measured repeatedly at baseline, 1, 3, 6, and 9 months, we will fit a repeated measurement analysis of covariance (ANCOVA) model with the four post baseline (1, 3, 6, and 9 months) FIQR total score as the response variables. The main predictors will be group (treatment arm), time (categorical), and their interaction. The model will be adjusted for baseline FIQR score. A random intercept will be used to adjust for the patient effect and to accommodate the correlation among the repeated measurements from the same patients. Another random intercept will be used to adjust for the potential clustering effect for patients in a specific yoga or exercise group. The primary analysis will evaluate the difference in FIQR score between the two treatment arms at 3-months (the primary end point) using appropriate contrast in this model. The sustained effect of intervention will be evaluated using appropriate contrast for the difference in FIQR change from 3-month to 6-month in this model.

D9d. Secondary analysis of primary outcome

For the FIQR total score, we will also define the patients with more than 30% reduction as “responders.” We will then compare the probability of responders between treatment arms using a generalized linear mixed model with a logit link. The responding status of each patient at **1, 3, 6, and 9 months** will be used as the outcome variables. Main predictors are group (treatment arm), time (1, 3, 6, and 9 months), and their interaction. A significant coefficient of group indicates a significant odds ratio of being a responder between the two arms at each time point. Each of the three domains of the FIQR score will be analyzed in the similar way to the total score.

D9e. Analysis of secondary outcomes

Since POYSE is not specifically powered for the secondary outcome, these results should be interpreted cautiously unless they are highly significant ($p < .001$). Pain severity as assessed by the Brief Pain Inventory will be analyzed using a repeated measurement ANCOVA model in the same way as the FIQR total score. BPI measurement at 1, 3, 6, and 9 months will be used as the response variable. Main predictors will be intervention group, time (categorical), and their interaction adjusted for the baseline BPI score. A random intercept of subject effect will be used to accommodate correlation within subject. Another random intercept of either a specific yoga or exercise group will be used to accommodate correlation within group (clustering effect for group delivered intervention).

Psychological symptoms: PHQ-9 score, GAD-7 will be analyzed using a repeated measurement ANCOVA model in the same way as the FIQR total score with repeated outcomes at 1, 3, 6, and 9 months as the response variables, the same set of main predictors and adjusted for baseline outcome measurement. The PTSD screening status will be analyzed using a generalized linear mixed model with a logit link. The main predictors will be intervention group, time (categorical) and their interaction adjusted for baseline PTSD screening status. PTSD severity from PTSD checklist for military will be analyzed similarly.

Other secondary outcome measures: The analytical strategy for other outcomes will be similar to the FIQR total score. These outcomes include SF-36, MFI, MOS Sleep Scale, Pain Catastrophizing Scale, Arthritis Self-Efficacy Scale, and PGIC.

We will employ several secondary analyses to assess the effectiveness of the treatment arms compared to each other in improving:

- Individual fibromyalgia symptoms (pain, fatigue, sleep quality, function)
- Health-related quality of life
- Patient global impression of change
- Pain beliefs and self-efficacy

Analytic techniques will be similar to those previously described. Since there will be a number of secondary outcomes, we will account for multiple-comparisons in analyses. We will use the Bonferroni approach to adjust for statistical significance threshold when the number of tests is less than 20. Otherwise, we will use the false discovery rate (FDR)¹²² to control the magnitude of false positives. We will also stratify our analysis based on a baseline depression status (PHQ-9). Our previous research indicated that 30% to 40% of patients will have clinically significant depression, which may adversely affect pain outcomes. Thus, depression is a potential moderator.

D9f. Missing data

Missing data are unavoidable in longitudinal studies. Based on our prior studies, we anticipate a possible dropout rate between 8% and 12%. However, we conservatively estimated a possible 20% drop out rate which is reflected in the sample size calculation. We will first run a logistic model with missing status as the response variable, intervention arm, patients’ demographic characteristics as covariates to check whether the missing status depends on the intervention group assignment and patient characteristics. Second, our linear mixed-effect model can accommodate missing-at-random (or

MAR which is assumed in many trials)¹²³ where no bias will be introduced by ignoring the missing-data mechanism. If drop-outs are Missing Not At Random (MNAR), meaning the likelihood of drop-out depends on an un-observed outcome, and the missing data mechanism is ignored, potential bias can be introduced. We will run sensitivity analyses using complete cases, last observation carried forward imputation, other multiple imputation methods including linear mixed-effect model, to compare results across these analyses to assess the robustness of the inference.

D9g. Economic evaluation

We will conduct cost effectiveness to determine if changes in health care utilization may offset the intervention costs between treatment arms. To conduct this analysis, we will use established methods¹²⁴ to estimate direct costs of the interventions and health care spending for study participants during the **9 month** trial period from the perspective of the VA.

D9h. Costing

We will use both micro- and gross (average) costing methods^{125,126} to estimate intervention and health care utilization costs, respectively. Applying VA Health Economics Resource Center (HERC) guidelines, we will measure intervention-related activities and their associated costs.¹²⁵ These intervention costs will include: 1) yoga and fitness instructor average salaries plus fringe benefits; 2) study materials (yoga mats, eye pillows, DVDs, audio-recordings, ergometers, heart monitors, pedometers) provided to intervention patients; 3) parking; and 4) facility overhead.

We will use VA DSS data to obtain health care utilization and cost estimates for trial participants. From the VA Patient Treatment File (PTF), we will collect hospital discharge date, days of hospital stay, and ICD-9 diagnoses (especially primary or secondary diagnoses) of fibromyalgia for each stay and determine the cost per admission. From the Outpatient Care File (OPC), we will collect dates of any outpatient visits for fibromyalgia, location of care (stop code), CPT codes assigned to each visit, and type of provider delivering care. We will classify all visits into rehabilitation, primary care, emergency, pain, specialty medicine or surgery, mental health, and other treatments based on clinic codes.

The number of outpatient prescriptions, especially for analgesic and psychotropic medications, will be found in the DSS NDE Pharmacy Datasets from VA Information Resource Center (ViReC).¹²⁷ Laboratory and x-ray testing will be collected to determine the number of tests for fibromyalgia evaluation and the costs per test. The cost of other care will be obtained from utilization data included in VA Austin databases. For non-VA care, covered by the VA, fee basis files will be merged into DSS data.¹²⁸ For non-VA care not covered by the VA, we will rely on patient self-report of outpatient visits and hospitalizations. Since VA utilization data does not include cost estimates, the above mentioned data sets will be merged to the HERC average cost datasets to estimate the costs associated with VA utilization for each participant.^{129,130}

D9i. Analysis

To estimate cost effectiveness, the dependent variable will consist of primary cost outcomes calculated from the VA health care system perspective. Having obtained the relevant VA healthcare utilization events, the healthcare event requires valuation, which is the task of assigning a reasonable market-level dollar for the expense amount. For each patient, outpatient events (visits, procedures, labs, medications, etc.) and inpatient DRGs and medical events (procedures, labs, medications, etc.) will be captured from these patient-specific administrative datasets. VHA databases provide sufficient outpatient and inpatient procedure and associated treatment classifications (by CPT-4, DRG and ICD-9 codes) to allow valuation. [name] has created similar datasets in other VA funded studies and publications. For health care utilization and the associated costs, we will compare inpatient days, outpatient visits, telephone care, number of prescriptions and radiographic tests. However, we may not be able to include inpatient costs because hospitalization may occur rarely during the 9 months of the trial and make estimates of between-group differences imprecise.

We will compare the two treatment arms with respect to total health care costs. Univariate, bivariate and regression techniques for repeated measures will be used to estimate the healthcare events and expenditure amounts. If cost data are skewed, log transformations will be performed prior to performing regression. An ANCOVA model will be used and contain treatment group (independent variable) and adjusted for comorbidities, age, and previous health care cost data collected at baseline as a covariate.

Costs will be reported in current year's dollars. Sensitivity analyses will be used to account for assumptions, including changes in intervention costs and changes in costs related to inpatient or outpatient services. If the interventions are found to be differentially more effective and costly, we will perform a cost-outcome analysis (i.e., incremental cost-effectiveness). We will estimate the effect of the interventions on the primary outcome (FIQR total score). The incremental cost to achieve a clinically meaningful decrease in FIQR total scores due to the interventions, i.e., the cost-effectiveness ratio, is calculated as the difference in intervention costs between the two treatment arms, divided by the difference in effectiveness between groups.

$$\text{Intervention Costs} + (\Delta \text{ Health Care Costs})$$

$$(\Delta \text{ FIQR}_{\text{Yoga}}) - (\Delta \text{ FIQR}_{\text{Structured Exercise Program}})$$

Where Δ FIQR = change in FIQR score, and Δ Health care costs = difference two groups

D10. PROJECT MANAGEMENT PLAN

D10a. Project Timeline

The 1st quarter in year 1 will involve hiring and training personnel. Important steps will include: (1) finalizing treatment protocols for yoga and exercise arms; (2) training the research assistant in screening, enrolling, and consenting study participants; (3) programming the electronic medical records to identify potential study subjects based on fibromyalgia diagnosis; and (4) obtaining permission from individual treating physicians to approach patients of theirs who might be eligible. During the next 2.5 years, we will enroll **306** participants (randomizing **153** to each group). Enrollment will average 10 per month. The **306** participants will be treated for 3 months. Participants will have outcome assessments at baseline, **1, 3, 6, and 9 months**. Thus, enrollment will be conducted from the 2nd quarter (year 1) until the 4th quarter (year 3); the intervention phase from 2nd quarter (year 1) until 1st quarter (year 4); and outcome assessments from 2nd quarter (year 1) until the end of study period. Baseline analysis will begin at the beginning of year 4 and conducted during the final 9 months of the study (separate baseline, 3 month, and end-of-study analyses). Main reports and manuscripts will be prepared in the 3rd and 4th quarters of Year 4.

POYSE Study Timeline																
Quarters	Year 1				Year 2				Year 3				Year 4			
	1	2	3	4	1	2	3	4	1	2	3	4	1	2	3	4
Start-up																
Enrollment																
Intervention																
Assessments																
Analysis																
Manuscripts																

D10b. Overall project coordination and facilities

Overall project coordination will be led by [name] (PI) and [name] (Project coordinator). [name] will coordinate all aspects of the project, trouble-shoot any problems, and provide regular updates on recruitment progress. Drs. [name], [name], and [name] have office, meeting and research space within the HSR&D Center for Implementing Evidence-based Practice (CIEBP) at the RVAMC. [name] and [name] offices are a 5-minute walk or drive, respectively from CIEBP. [name] will be available for the monthly study-related teleconferences.

D10c. Investigator roles

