The standardized sequence of yoga poses will be introduced to participants. **Appendix 2** outlines the full array of poses to be used. The poses will begin in the seated position and consist of five poses that involve “breathing with movement” (head moves, scapula, and directions of the spine, pinwheel and pendulum). Additional poses will include: “table,” “cat cow,” “sunbird,” “downward dog,” “cobra,” “locust,” and “bridge.” [name] will encourage the safe performance of physical poses and tailor them to participants’ needs and abilities. For patients with fibromyalgia, poses will avoid the extremes of range of motion. All sessions will end with a yoga *nidra* (“yogic sleep”) exercise to develop both deep relaxation and full alertness.

Deep breathing exercises will be taught and emphasized throughout every session. “Connecting with the breath” is a common theme in yoga and is combined with the poses (“breathing with movement”) to facilitate yoga practice. An effective breathing technique (alternate nostril breathing) will be taught to participants. All yoga sessions will include at least 10 minutes of relaxation, using progressive relaxation techniques. The relaxation component will be completed lying supine and aided with an eye pillow and yoga mat for each participant. The relaxation is based on resting the “physical body.”

Participants will be encouraged to exercise according to their limits, rather than rigid adherence to posture techniques. The yoga intervention will be tailored to the individual. It will include low intensity, low impact modified poses adapted with pathophysiologic changes of fibromyalgia in mind.⁸² For example, and repetitive muscle movements will be minimized to reduce the potential for muscle micro-trauma theorized to occur in fibromyalgia patients. In addition, [name] will encourage slow transitions from lying to standing to minimize dizziness and lightheadedness related to autonomic nervous system changes associated with fibromyalgia. Peripheral pain generators such as knee osteoarthritis, back pain, and carpal tunnel symptoms will be minimized by adapting standing poses to sitting or lying poses or using bolsters or pads. Previous studies that involved high intensity, repetitive exercises reported high rates of attrition or worsening fibromyalgia symptoms.^{62, 82, 83} Tailoring of poses in POYSE is expected to yield lower attrition rates.

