Participants will undergo a graded aerobic exercise program; the preferred exercise prescription to reduce the possibility of exercise-induced pain.^{48, 84-86} The exercise program will start at a low intensity, last for a short period of time, with gradual increases in exercise intensity and duration. Participants will start exercising at a slow pace for 5 minutes to warm-up. For each 5-minute phase (total of 30 to 35 minutes total per session), the exercise intensity will be gradually increased to the mid-range of their exercise prescription.

During the first exercise session, the fitness instructor will provide an introduction and overview of the exercise program. Veterans will also receive instructions on how to use the heart rate monitor, pedometer, and how to rate their perceived exercise exertion according to the Borg scale. In addition, veterans will learn how to keep an activity diary at home and how to select physical activities and exercises based on heart rate, perceived exertion, or metabolic energy costs. Further, subjects will have their blood pressure and heart rate monitored during all sessions. Subjects will be asked to report any cardiovascular symptoms such as shortness of breath or chest pain while exercising. If a subject experiences any cardiovascular symptoms or an unsafe blood pressure or heart rate the instructor will call an ambulance to transport the subject to the VA ER for immediate medical assessment.

Exercise sessions with other participants and the fitness instructor will last approximately 75 minutes and occur once a week for 12 weeks; the same session schedule and duration as the yoga arm. The fitness instructor will teach participants to use a table-top ergometer at a sub-maximal level, determine baseline fitness, and develop an individualized exercise prescription. The fitness instructor will provide educational tips on exercise and selection of physical activities. The instructions will be informed by veterans' heart rate (at baseline and at different exercise levels), their ratings of perceived exertion, and metabolic activity (METS). While we will employ individualized exercise prescriptions for veterans

randomized to the structured exercise program (SEP) arm, the SEP will be delivered in a group/class format to control for the potential benefits of social interactions and attention across treatment arms.

D7g. Exercise ergometer starting point, perceived exertion, and metabolic activity

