In general, participants will start exercising with the ergometer at a power of 30 watts for 5 minutes, followed by increases of 15 watts every 5 minutes until veterans reach their sub-maximum target heart rate $[(220 - \text{age}) \times 0.85]$. After each 5-minute phase, heart rate, blood pressure, and a rating of perceived exertion will be recorded. To obtain ratings of perceived exertion, veterans will be evaluated according to the Borg Scale,⁸⁷ which ranks exertion ordinally (“very, very light” to “very, very hard”). These terms are assigned a number from 7 to 20. If the target heart rate is not reached, the test will be stopped at a score of 17 (“very hard”). We want participants to exercise with the ergometer at a level associated with a perceived exertion of 12 on the Borg Scale, i.e. the level below “somewhat hard” for the prescribed duration while wearing a heart rate monitor. This level is consistent with light-to-moderate exercise recommended in the fibromyalgia literature.^{48, 84-86}

Combining perceived exertion with the structured exercise program allows veterans to better gauge their “comfort zone” and select physical activities based on how they feel on any given day. Heart rate monitoring provides useful information for our fitness instructor and veterans to set their exercise intensity based on different levels of exercise. Energy output data from the sub-maximal test will be converted to equivalent energy costs in metabolic activity (METS). The METS will then be benchmarked for a wide variety of recreational and occupational activities relevant to the veteran.

D7h. Schedule and content of weekly exercise sessions

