Health Care Utilization and Costs: will be assessed at the end of the 9 month study period for each patient using data available in CPRS. This will include all outpatient, rehabilitation, and emergency room visits, inpatient days, x-ray and lab tests, medical and surgical consultations, and medications.

D9. STATISTICAL CONSIDERATIONS

POYSE will involve a 2-arm, parallel group, randomized comparative effectiveness trial. Since participants cannot be blinded to treatment assignment, observed outcomes (if positive) could be affected by expectation bias. To account for this potential bias, we will assess treatment expectations at baseline and account for expectations in our analyses. We will randomize at the patient rather than the provider level for two reasons: (1) randomization at patient level saves sample size; and (2) patients from the same provider in the two arms will adjust for “provider effect.” Contamination will also be low because there is relatively minimal involvement required of VA providers in POYSE. In addition, randomization will be stratified by sex (women or men) and **study recruitment site (VAMC or CBOC)** to avoid potential imbalance of these factors between the two arms. [name], PhD (statistician) will create a randomization chart to randomize patients in **blocks of 4 or 6**.

D9a. Sample size

Our sample size is calculated based on estimated differences of intervention effects between two arms on the primary outcome; Fibromyalgia Impact Questionnaire Revised (FIQR) total score at 3 months.

The FIQR total score is a continuous measure: a 0-100 scale and reflects the average of three domains: function, overall impact, and symptoms. In a recently published yoga trial for patients with fibromyalgia, Carson et al.⁶¹ found a pre-treatment FIQR score of 48.3 (standard deviation = 17.5).

Post-treatment scores were reduced by 31% (FIQR = 35.5, SD = 17.6, effect size = 0.72) from the yoga intervention. In an earlier trial, Mannerkopi et al.¹¹⁸ tested an intervention combining pool exercises with

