outcome assessments. We will establish a local Data Safety Monitoring Board (DSMB) that meets every 6 months during the study and is notified via email of all deaths and SAEs at the time of local IRB notification. Members will consist of non-study investigators and will include a pain specialist, a rheumatologist, a clinical trialist, a nurse, and a biostatistician.

The DSMB will monitor the following: (a) subject recruitment, accrual, and retention; (b) patient outcomes and adverse events; (c) subject safety, privacy, and confidentiality procedures; (d) diversity of subject enrollment (i.e., sex and race); (e) data quality and major findings in terms of treatment benefits and risks; (f) results of related studies that impact subject safety; (g) assessment of scientific reports that might alter the benefit/risk ratio of the study. Analyses of data will be performed by the study biostatistician but will be independently interpreted by the DSMB (which will include an independent biostatistician) which can request additional analyses as the DSMB members see fit. Since this is an effectiveness trial using evidence-based treatments, there are no pre-planned interim analyses or stopping rules. The DSMB will submit the report of its annual meeting to the study investigators who will in turn report the information to IRB in its continuing review, unless there are items DSMB feels should be reported to IRB immediately.

D11. DISSEMINATION AND IMPLEMENTATION PLAN

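### Vital-sign checks, symptom prompts and the ambulance rule are written only for exercise classes and no common adverse-event method is given, so non-serious harms would be ascertained unequally and emergency visits could be induced in one arm

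*Combined protocol and SAP*

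**What the plan says.** Section D7f (exercise classes) sets three procedures. First, "subjects will have their blood pressure and heart rate monitored during all sessions". Second, "Subjects will be asked to report any cardiovascular symptoms such as shortness of breath or chest pain while exercising". Third, if such a symptom occurs, or if blood pressure or heart rate is unsafe (a term left undefined), "the instructor will call an ambulance to transport the subject to the VA ER for immediate medical assessment". Section D7g adds, for the ergometer, "After each 5-minute phase, heart rate, blood pressure, and a rating of perceived exertion will be recorded". The exercise session log at the end of the document has a row for blood pressure and entries for heart rate. Section D7h adds calls at months 4, 5 and 6, described only for the exercise arm.

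The yoga sections (D7a to D7e) give preventive coaching. In D7c the therapist "will encourage slow transitions from lying to standing to minimize dizziness and lightheadedness". They describe no measurement in class, no symptom question and no response rule. The class schedule in Appendix A lists practices only.

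Section D10e covers both arms. It refers to frequent contacts with subjects, close monitoring of side effects, monthly investigator meetings, and notification of deaths and serious adverse events to the DSMB. The DSMB also reviews adverse events and "data quality and major findings in terms of treatment benefits and risks". No instrument, question set or frequency is given, and the table of measures has no adverse-event item.

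For Aim 3, section D8c takes utilization from the VA record for every patient: "This will include all outpatient, rehabilitation, and emergency room visits". Section D9i compares total health care costs between arms, and the cost-effectiveness ratio carries the difference in health care costs in its numerator.

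**The concern.** Two separate problems follow.

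The first is ascertainment. If the same symptom or abnormal reading occurs equally often in both kinds of class, the exercise arm has a procedure that finds and records it. The yoga arm depends on a volunteered remark or an unstructured contact. A between-arm table of non-serious harms, whether seen by the DSMB or published, would then make exercise look less safe without any true difference.

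The second is induction of cost. The exercise-only rule can generate VA emergency visits that would not otherwise have happened, and the cost analysis has no means of identifying them. They would raise health care cost in the exercise arm. Both effects run in favour of yoga, the arm that the protocol expects to do better.

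**Working it through.** The plan states no figure for this point, so the check is first a comparison of the text and then an illustration of scale.

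**Text, side by side**

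| Element | Exercise (D7f–D7i) | Yoga (D7a–D7e) | Both arms |
|---|---|---|---|
| Blood pressure and heart rate in class | Every session; each 5-minute ergometer phase | None described | None in class; blood pressure and pulse in the Functional Assessment at baseline, 3 and 6 months |
| Symptom prompt | Cardiovascular symptoms | None described | General monitoring in D10e, no form or timing |
| Response rule | Ambulance to VA emergency room | None described | None |
| Serious events | – | – | Notified to the DSMB (D10e) |
| Emergency visits | – | – | From VA data (D8c, D9h) |

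The last two rows are symmetric. The first three are not, and the provisions in the right-hand column do not even them out: readings at two follow-up visits cannot capture what happens in a class.

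**Exposure to checks**

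Inputs: 153 per arm (D9a); 12 weekly sessions (D7f).

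- Scheduled exercise person-sessions: 153 × 12 = 1,836, a ceiling that assumes full attendance. None is described for yoga.
- If 80% of sessions are attended (an assumption): 0.80 × 1,836 ≈ 1,469.

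**Unequal detection, equal true risk**

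Assumptions, not document figures: detection of 80–90% under exercise and 50–70% under yoga. With equal true risk, the ratio of recorded events is the ratio of the detection probabilities.

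- Smallest: 0.80 / 0.70 = 1.14
- Largest: 0.90 / 0.50 = 1.80

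Expected recorded events are 153 × true risk × detection:

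| Assumed true risk | True events per arm | Recorded, exercise | Recorded, yoga |
|---|---|---|---|
| 5% | 7.7 | 6.1–6.9 | 3.8–5.4 |
| 10% | 15.3 | 12.2–13.8 | 7.7–10.7 |
| 20% | 30.6 | 24.5–27.5 | 15.3–21.4 |

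If someone tested such a table (two-sided 5%, 153 per arm, detection 0.9 against 0.5), the chance of a spurious significant result would be about 16%, 28% and 52% at true risks of 5%, 10% and 20%. At 0.9 against 0.7 it would be about 7%, 9% and 16%.

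**Induced emergency visits**

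Assumption: the rule is triggered in 0.1% to 2% of exercise sessions.

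- 1,836 × 0.001 = 1.8 and 1,836 × 0.02 = 36.7, so about 2 to 37 visits
- Per exercise participant: 12 × 0.001 = 0.012 to 12 × 0.02 = 0.24

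The documents give no unit cost for an emergency visit, so no dollar figure follows.

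**The case against.** The strongest reply is that safety monitoring is not one-sided. D10e applies to every subject. Both arms have the same blinded assessments, including pain and global change at 1, 3, 6 and 9 months, and serious events reach the DSMB from either arm. A reader might infer from D7f that harms in yoga will surface only by chance; D10e does not support that. What stands is narrower: D10e does not say how or when non-serious events are asked about, so it does not make collection equal.

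A reader might also infer that emergency costs are detected better under exercise. They are not, because VA records serve both arms. The issue is visits that the rule itself creates. It can be argued that these are real costs of delivering the programme from the VA perspective. That is a fair position, and it is why both versions should be shown instead of one being dropped. D9i plans sensitivity analyses on costs, but none that isolates these visits. D9h speaks of outpatient visits for fibromyalgia, which read narrowly might omit some of them; D8c and the total-cost comparison in D9i point the other way.

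It is tempting to say that the ambulance trigger is easily met, because the D7g test runs to 85% of predicted maximum heart rate or to a Borg score of 17. The documents do not establish this. Training is aimed at Borg 12, chest pain or dizziness with exercise is excluded at entry, and reaching a target heart rate is not stated to be unsafe. The two sections do not say how they relate.

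Three further points stand. No formal between-arm harms analysis is planned, so the bias bears on DSMB review and later reporting. Closer observation of exercise may be justified, and nothing here asks for its removal. Some of the document (part of D10, the consent pages and several cited appendices) was not available, so yoga safety text there cannot be ruled out.

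**Conclusion.** The concern holds in limited form. On the available text, following the plan exactly gives unequal ascertainment of non-serious harms, chiefly cardiovascular findings in class, and permits emergency visits to be induced in the exercise arm alone.

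Only the ceiling of 1,836 person-sessions comes from the documents. The false ratio of 1.14 to 1.8 and the 2 to 37 induced visits rest on assumed rates. The ratio applies only to events whose detection depends on the exercise-class procedures; over all harms it would be diluted.

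A reader might go further and infer that the primary result is compromised. It is not: the FIQR at 3 months is collected by the same blinded interview in both arms, and the sample size does not depend on this point. The point is worth correcting because the remedy is cheap and because the DSMB and Aim 3 would otherwise rest on collection, or on costs, that differ by design.

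**What to change.** 1. Use one short, identical, self-completed adverse-event form in both arms, at each weekly class and at 1, 3, 6 and 9 months. Return it to existing unblinded study staff, not to the outcome assessor. Asking these questions in the blinded interview, even after the FIQR, would protect only that interview: a complaint about a pose or an ergometer at 1 month could reveal the arm before the 3-month primary assessment.
2. Base any between-arm comparison of harms, including tables for the DSMB, on that form alone. Report findings from exercise-only monitoring separately. Serious-event notification under D10e continues unchanged.
3. Flag emergency transports triggered by the protocol, and report the cost comparison and the cost-effectiveness ratio with and without them.
4. The investigators should reconcile the response rule in D7f with the test procedure in D7g and state what applies in yoga classes. What that rule should be is for them to decide.

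The cost is a brief extra form for participants, which can travel with the home-practice records already collected weekly in both arms, one flag in the cost file and one extra sensitivity analysis. No extra visits or staff are needed.
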